 - History of chronic kidney disease or estimated glomerular filtration rate <60 ml/min/1.73m²
 - History of diabetes or non-fasting glucose >200 mg/dL
 - History of major depressive disorder (PHQ-9 score ≥15) or psychosis
 - History of ulcer diseases, including esophageal-gastric ulcer
 - History of malignancy in the past 5 years
 - History of liver disease
 - History of organ transplant
 - History of Addison's disease (adrenal insufficiency)
- Use of medications which may alter serum potassium levels or in which potassium supplementation is contraindicated: antihypertensive agents, antihistamines, antiparkinson agents, antimuscarinic agents, antipsychotics, muscle relaxants, systemic corticosteroids, or chronic use of non-steroidal anti-inflammatory drugs
- Serum potassium ≥5.0 mEq/L
- Metabolic acidosis
- Consumption of >85th percentile of usual potassium intake among US adults (>3,750 mg/day)^{29,32}
- For women, current pregnancy, breastfeeding, or plans to become pregnant during the study
- Consumption of ≥21 alcoholic beverages per week or consumption of ≥6 beverages per occasion
- Current or planned residence making it difficult to meet trial requirements or travel to the study site
- Current participation in another intervention or pharmaceutical trial
- Unable or unwilling to complete 24-hour BP or urinary sample collection
- Other concerns regarding ability to meet trial requirements, at the discretion of the investigators or staff

2C. Recruitment

Participant recruitment will be facilitated with support from the Tulane University Translational Science Institute's Clinical Research and Community Engagement Core. The investigative team has substantial experience with recruitment for both clinic trials and epidemiological studies. Based on this experience, we are keenly aware of the importance of recruitment and believe that we will have the appropriate population to fulfill our recruitment goals. In this study, we aim to recruit adults with elevated BP or hypertension from the greater New Orleans, LA metropolitan region, primarily from mass mailings targeting zip codes proximal to the study center. We also have several contingency plans.

Our recruitment strategies include:

Primary

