Table 3. Study Visit Schedule and Data Collection								
	Pre-screen	SV/ BV1	SV/ BV2	RZ	1- wk Call	6-wk visit	12-wk visit 1	12-wk visit 2
Verbal consent and eligibility	X							
Written informed consent		X						
Eligibility confirmation				X				
Demographics		X						
Social and behavioral factors			X					
Medical history, medications		X				X	X	
Height (SV1), weight, waist circ.		X				X	X	
24-hour dietary recall*		X				X	X	
3 office BP measurements		X	X			X	X	X
24-hour urinalysis		X	X	Confirm		X	X	X
Non-fasting blood samples		X				X	X	
Ambulatory BP monitoring			X	Confirm		X	X	Confirm
Symptoms assessment			X		X	X	X	
Dispense medication				X		X		
SV/BV=screening and baseline visits and RZ = randomization visit; *Two 24-hour dietary recalls, the first in-person and the second by telephone. 24-hour urine and ambulatory BP measures will be evaluated for completion and confirmed prior to randomization into the trial.								

Pre-screening: For in-person and telephone pre-screening visits, verbal consent will be obtained from potential participants who will then be assessed for basic eligibility. When conducting pre-screening in community settings, blood pressure measurements will be obtained to assess eligibility. After determining basic eligibility, potential participants will be scheduled for the first screening visit.

Screening/baseline visits: At screening visit 1, we will obtain written informed consent for the trial and measure height, weight, BP, obtain a medical history and medications list, and collect a blood sample for a basic metabolic panel. Two 24-hour dietary recalls will be conducted to assess eligibility based on dietary potassium intake, with 1 in-person and 1 via telephone. Individuals will be instructed on collecting a 24-hour urine specimen and asked to bring it to the clinic for screening visit 2. At screening visit 2 (between 3 and 14 days from first screening) we will measure BP, assess baseline symptoms, and confirm eligibility. Each participant will be fitted with an ambulatory BP monitor (ABPM) and receive instruction on its use. Individuals will be instructed to collect a second 24-hour urine specimen and return it and the ABPM 24 hours after screening visit 2.

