Potassium supplementation may lead to adverse effects, including nausea, gastrointestinal discomfort, and hyperkalemia in participants taking certain antihypertensive medications or having comorbidities associated with impaired potassium excretion (e.g. heart failure, decreased renal function). However, meta-analyses suggest potassium supplementation of 17-140 mmol/day is safe with few side effects, primarily gastrointestinal discomfort.^{29,34-36} Short-term supplementation up to 120 mmol/day (total urinary potassium excretion 167-225 mmol/day) has been used in RCTs without significant side effects in various patient populations.³⁷⁻⁴⁰ Hyperkalemia-related adverse events are associated with acute ingestion of extremely high doses of potassium (>200 mmol/day beyond usual intake), impaired renal function, and antihypertensive medications use,²⁹ but are rare in the general population.^{41,42} Hyperkalemia was not observed in short-term potassium loading studies conducted in healthy volunteers that employed doses up to 400 mmol/day.⁴⁴⁻⁴⁶ We expect our interventions to be safe and well tolerated because we will include only unmedicated adults consuming <85% of usual potassium intake among US adults, and having normal renal function.^{29,42}

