Minimization of Risk: We will include only unmedicated adults consuming <85% of usual potassium intake among US adults, and having normal renal function and serum potassium levels (<5.0 mEq/L). The maximum dose will be 90 mmol/day and participants will be monitored for side effects. We will closely monitor potential adverse events according to the protocols below. An experienced study physician ([name]) will evaluate safety concerns throughout the trial. During follow-up, study staff will collect data on side effects via a safety questionnaire form at each visit and 1 week post-randomization. At the first screening visit, 1-, 6-, and 12-week visits, we will administer symptoms questionnaires, which will consist of a checklist to identify participant complaints. Participants will be encouraged to contact the study team if they experience any new symptoms. Additionally, at the 6- and 12-week visits, we will conduct blood tests to evaluate serum sodium and potassium levels. Severe adverse events will be promptly reported to the Data and Safety Monitoring Board (DSMB). Management of adverse effects will be based on the protection and safety of the participant. If severe adverse effects are reported by a participant, potassium supplementation will be examined and altered in order to mitigate the adverse effect. In any extreme cases, participants will be instructed to stop the intervention.

There is a small risk of bruising and a rare chance of local infection associated with standard venipuncture to collect blood samples.

Minimization of Risk: Our proposed study will employ trained and certified study staff and phlebotomists to minimize adverse events associated with venipuncture.

There is a potential risk of unauthorized disclosure of medical information.

Minimization of Risk: This risk will be prevented by using a strict protocol for data processing and by the appropriate training of all study personnel. Confidentiality of all data collected during the study will be maintained through the use of unique, encrypted study identification (ID

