Any adverse event that meets any of these criteria will be documented and reported as a serious adverse event. Participants will be queried for side effects and AEs at the 1-week telephone visit and each clinic visit (week 6, week 12). In addition, information on serious adverse events may also be reported to study staff spontaneously by participants between study visits. In addition to local reporting requirements, all serious adverse events will be recorded by clinic staff and forwarded to the study physician within 72 hours of knowledge of the event. SAEs will be collected and reported from screening to the end of the study follow-up period for an individual participant. SAEs will be followed until resolution, stabilization, or until it is determined that study participation is not the cause. The Principal Investigator will be responsible for timely reporting to the NIH and the DSMB. The Principal Investigator will provide reports of serious adverse events for review by the DSMB at their meetings.

In addition, standard clinical safety alerts will be employed. When a measurement attains a defined alert level as described in the bullet points below, study staff will immediately notify the study physician for further evaluation.

- Systolic BP >180 or diastolic >110
- Heart rate <40 bpm
- Serum potassium ≥ 6.0 mEq/L or ≤ 3.0 mEq/L
- Serum sodium <130 mEq/L or >155 mEq/L
- Serum total bicarbonate <15 mEq/L or >40 mEq/L
- Serum calcium <8 or >11 mg/dL

- Plasma glucose <50 mg/dL or >350 mg/dL
- Serum creatinine doubling from last value
- CBC hemoglobin <7.0 gm/dL
- “Acute Distress” (includes chest pain or other signs or symptoms constituting an emergency)

5. Benefits

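### A week-6 potassium of 5.0 to <6.0 mEq/L, or an eGFR below 60 without creatinine doubling, would have barred entry but triggers no required study-physician review

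*Combined protocol and SAP*

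**What the plan says.** **Entry (section 2B).** Two of the exclusions are "Serum potassium ≥5.0 mEq/L" and "History of chronic kidney disease or estimated glomerular filtration rate <60 ml/min/1.73m²". Section 4A presents the same conditions as part of how risk is minimized, describing the participants as "having normal renal function and serum potassium levels (<5.0 mEq/L" mEq/L). It also links hyperkalemia to people "having comorbidities associated with impaired potassium excretion (e.g. heart failure, decreased renal function").

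**On treatment (section 4B).** When a measurement reaches a listed alert level, "study staff will immediately notify the study physician for further evaluation". The potassium alert is "Serum potassium ≥ 6.0 mEq/L or ≤ 3.0 mEq/L". The only kidney alert is "Serum creatinine doubling from last value". No eGFR level is listed, although section 3E says eGFR will be calculated from serum creatinine.

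**Timing.** Section 3E schedules the metabolic panel at the first screening visit, week 6 and week 12. In Table 3 the row "Dispense medication" is marked at the randomization visit and again at the 6-week visit.

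**Changing the dose (section 4A).** Supplementation is examined and altered when a participant reports severe adverse effects. Tablets are stopped in extreme cases, which are not defined.

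**The concern.** The protocol treats potassium below 5.0 and normal kidney function as conditions that make up to 90 mmol/day of extra potassium acceptable. It does not say who must look when a participant no longer meets them on treatment. Week 6 is the only scheduled blood test between randomization and week 12, so it is the one laboratory checkpoint that can still change exposure. Staff who follow the numeric alert list exactly could leave a potassium of 5.8 unreviewed by the study physician while dosing continues for the second six weeks. What is at stake is participant safety; the validity of the primary comparison is not in question.

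**Working it through.** **1. Limits side by side**

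| Measure | Bars entry (2B) | Requires physician notification (4B) | No rule between |
|---|---|---|---|
| Serum potassium | 5.0 or more | 6.0 or more, or 3.0 or less | 5.0 to <6.0, a band of 6.0 - 5.0 = 1.0 mEq/L |
| Kidney function | eGFR <60 | creatinine doubled from last value | eGFR <60 without doubling |

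**2. Size of the kidney gap.** Assumption, not in the documents: eGFR varies as creatinine to the power -p, with p from 1.0 to 1.2. The creatinine ratio needed to fall from baseline B to eGFR E is (B/E)^(1/p).

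- 75 to 60: 1.25 (p = 1.0) or 1.20 (p = 1.2), a rise of 20-25%.
- 90 to 60: 1.50 or 1.40, a rise of 40-50%.
- 75 to 45: 1.67 or 1.53, still short of doubling.
- Starting at 75, eGFR when creatinine has just doubled: 75 × 2^-p = 37.5 or 32.6.

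The alert needs a rise of 100%. The example of 45 depends on the starting value. Creatinine has doubled by the time eGFR reaches 45 if baseline was at least 45 × 2^p = 90 (p = 1.0) or 103 (p = 1.2). From those baselines upward the existing alert fires.

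**3. Search for another rule.** These are the other places where the protocol could catch such a result:

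- 3D, midterm visit: serum potassium is assessed; no level or action is given.
- 3C: the study physician monitors side effects, and the DSMB reviews cumulative data.
- 4A: the study physician evaluates safety concerns throughout. Dose alteration follows a participant's report of severe effects, which a symptom-free laboratory value does not meet.
- 4B: a clinically significant laboratory finding is an adverse event, but forwarding to the study physician is specified for serious events and listed alerts.
- Section 5: clinically abnormal values go to primary care; the term is undefined, and referral is not a tablet decision.

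None sets a potassium or eGFR level below the alerts, and none ties the second supply to the week-6 result.

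**4. What a review rule could cost in power.** Inputs from 3G and 3I: 47 evaluable per arm, SD 7 mm Hg, mean changes 0, -1.5, -3, -4.5, contrast -3, -1, 1, 3, two-sided 0.05.

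The plan's own figure first: contrast = 1.5 - 3 - 13.5 = -15.0; SE = 7 × √(20/47) = 4.566; noncentrality = 15.0/4.566 = 3.285; df = 4 × 47 - 4 = 184; power 90.5%. This agrees with the stated 90%. Then 47/0.85 = 55.3, so 56 per arm and 224 in total, as stated.

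Now let an assumed share f of the 60 and 90 mmol arms change dose:

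| Action | f | Contrast | Power |
|---|---|---|---|
| Stop, effect fully lost by week 12 | 2% | 1.5 - 2.94 - 13.23 = -14.67 | 89.2% |
| Stop, effect fully lost by week 12 | 5% | 1.5 - 2.85 - 12.825 = -14.175 | 87.0% |
| Step down 30 mmol/day (lose 1.5 mm Hg) | 2% | -15 + 4 × 0.03 = -14.88 | 90.0% |
| Step down 30 mmol/day (lose 1.5 mm Hg) | 5% | -15 + 4 × 0.075 = -14.70 | 89.3% |

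The 30 mmol arm is left unchanged here. If the same share stopped there too, the contrast would be -15(1 - f), which is -14.25 at 5%. That is slightly less loss than the -14.175 above.

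**The case against.** The best defence is that the study physician already has a standing role: monitoring side effects (3C), evaluating safety concerns throughout the trial and stopping tablets in extreme cases (4A). The sponsor also explains why few events are expected. Participants are screened and unmedicated, the top dose is 90 mmol/day, and the cited evidence is described as showing that 17-140 mmol/day is safe and that hyperkalemia was absent in short loading studies up to 400 mmol/day. This stands as a reason for routine review over automatic stopping. It does not close the gap, because nothing requires a value in the uncovered range to reach the physician.

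A reader might infer that 2B and 4B contradict each other. They do not: entry limits may properly be stricter than limits for an urgent call.

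A reader might also infer that the plan requires tablets to continue, or that abnormal results get no attention. Neither is supported. Continuation is left to discretion, and general follow-up routes exist.

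Finally, the Manual of Procedures described in 3F is not among the documents and may hold further rules. The point is therefore about the protocol text only.

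**Conclusion.** The point holds as a narrow gap in the safety rules. For potassium it is the band from 5.0 to <6.0 mEq/L. For kidney function it is an eGFR below 60 reached without creatinine doubling. The kidney figures rest on the assumed power relation between creatinine and eGFR, and an eGFR of 45 goes unflagged only for baselines below about 90-103. The power figures rest on assumed shares of 2% and 5%. The documents give no basis for estimating how many participants would be affected.

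It would go too far to read 5.0 mEq/L as a level at which dosing must change. The documents establish it as an entry limit only, so it can support a review trigger and no more. Nothing here alters the sample size or the primary analysis.

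**What to change.** Add to section 4B, in substance: any week-6 serum potassium of 5.0 mEq/L or more, or eGFR below 60, is sent to the study physician for non-urgent review. The physician decides on repeat testing and on continuing, reducing or stopping tablets, and continued use of the second supply is subject to that review. No dose change is automatic.

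Three supporting points:

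- Keep the existing 6.0/3.0 and doubling alerts as immediate calls.
- Make any dose change through the unblinded dispensing staff or the research pharmacy. Section 3D places the unblinded staff member at randomization, so the text must extend that role to week 6. In the 30 mmol arm, a reduction of 30 mmol/day means stopping.
- Analyse participants in their randomized group, as 3I already provides.

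This is a cheap improvement: a few sentences and a REDCap flag on results already collected. Its costs are:

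- a few extra notifications, some from measurement scatter or from placebo participants;
- partial clues to allocation for the physician, since flags would be likelier in the higher arms;
- an unblinded dispensing step at week 6;
- the small loss of dose separation shown in the working.
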